6.1.1 Administration of Intervention

The Relay intervention consists of two components, both administered by the peer navigator. The first component is delivered in-person in the ED after the patient has been medically stabilized. The peer navigator then obtains the patient's contact information and makes plans to follow up over the next 90 days. Follow-up visits are provided in person or by phone with a Relay peer navigator. The exact services, mode, timing, frequency, and duration may depend on individual participant needs and desire to participate. The intervention is administered by DOHMH. The NYU study investigators are not administering the intervention.

6.1.2 Procedures for Training Interventionists and Monitoring Intervention Fidelity

Relay peer navigators receive thorough training and ongoing supervision from DOHMH. DOHMH may change training protocols without approval from the study investigators. The study investigators are not responsible for training Relay peer navigators. Currently, a standardized approximately 3-day new hire orientation and training covers all facets of the Relay program including OD education, naloxone distribution, MOUD, treatment referrals, tenets of peer navigation, building relationships, assessing and addressing patient needs, and documentation of patient contacts. Peer navigators additionally receive approximately 24 hours of formal training in motivational interviewing. Peer navigators meet with supervisors (Licensed Masters-Level Social Workers or Mental Health Counselors) regularly and participate in monthly group supervision meetings for ongoing training, program updates, and presentation of difficult cases. Supervisors also provide assistance and individual support for difficult cases. Additionally, peer navigators receive training in self-care and participate in voluntary group sessions with an external social worker to discuss any frustrations, stress, feelings, and emotions regarding their Relay work.

CONFIDENTIAL

This material is the property of the NYU School of Medicine and NYU Langone Health. Do not disclose or use except as authorized in writing by the study sponsor
Behavioral Intervention Template Version: 11 January 2019

Study staff: Study RAs will complete privacy and security, HIPAA, and human subjects protections trainings. RAs will be employees of NYU School of Medicine as well as the study sites (for baseline visits at those site EDs). All RAs will receive standardized, thorough training in the study procedures prior to beginning work on the study. All RAs will receive ongoing supervision from the study Project Manager under direction from the PIs and Site PIs.

Fidelity monitoring of intervention: We will assess fidelity as follows: 1) All participants will complete an RA-administered exit survey interview at the conclusion of the baseline visit (in some cases the exit survey may be completed by phone the next day). The exit survey will assess what interventions the participant received in the ED that are relevant to opioid OD (e.g. substance use screening, OD education, naloxone kit(s) received, treatment referral/follow-up offered). The exit survey interview will also ensure that SDC arm participants receive, at a minimum, OEND, a list of treatment programs, and a handout with Relay program information. RAs will need to check off boxes in the exit survey indicating that the participant has received these items. Participants will also be asked at follow-up assessments what additional Relay program services they have received in the interval since the last assessment, 2) After each participant contact, Relay peer navigators complete content checklists to capture the duration of the interaction and activities performed during the session. To minimize burden to DOHMH and the peer navigators, the study will use the existing peer navigator contact content checklists used by DOHMH. Throughout the study, we will use this data to assess intervention dose, measured using the number, type (phone or in-person conversation, accompaniment to appointments), and duration of contacts; this information is routinely logged by the Relay peer navigator for DOHMH, as part of regular program activities. We will obtain a MOU/DUA to use these checklists to assess study fidelity.

6.1.3 Assessment of Subject Compliance with Study Intervention

Consistent with the motivational interviewing approach, participants who do not comply with the study intervention (e.g., decline referrals or decline to set substance use risk reduction goals) remain in the Relay intervention, and the peer navigator continues to offer support. Participant receipt of intervention components will be tracked both through self-report assessments and through Relay program data.

7 Study Procedures and Schedule

7.1 Study Procedures/Evaluations

Study procedures/evaluations in this protocol include: screening, consent, enrollment, randomization, research interviews (self-reported assessments and semi-structured qualitative interviews), overdose prevention education, as well as data extraction from administrative data sets and Relay programmatic data. All participants receive standard medical care in the ED. Those in the Relay intervention arm additionally receive the DOHMH Relay program, and those in the SDC arm additionally receive RA-delivered OD prevention education. There are no laboratory results, biospecimens, or images collected as part of this research protocol.

7.1.1 Study Specific Procedures Overall

- Eligibility assessment and study consent
- Randomization to study arm
 - Relay intervention: peer navigator administered OEND, motivational counseling, referrals and support and linkage to services while in the ED and for up to 90 days post-discharge.
 - Site-directed Care: RA will ensure that participant receives, at a minimum, overdose prevention education consisting of OEND, treatment program list, and Relay informational handout.
- Administration of questionnaires for patient-reported outcomes, at baseline, 1-month, 3-months, and 6-months.
- Baseline exit survey documenting opioid-related services received by the participant in the ED.
- Collection of participant information (to allow linkage with administrative data)
- Collection of participant locator form information

CONFIDENTIAL

This material is the property of the NYU School of Medicine and NYU Langone Health. Do not disclose or use except as authorized in writing by the study sponsor

Behavioral Intervention Template Version: 11 January 2019

- Data extraction from administrative datasets including vital statistics / mortality data, DOHMH OD deaths data, and health services use data (which may include Regional Health Information System [RHIO], Statewide Planning and Research Cooperative System [SPARCS], Medicaid, and electronic medical record [EMR] data, as available)
- Semi-structured qualitative interviews with Relay participants, peer navigators, and ED staff.
- Assessment of study intervention adherence (Relay contact content checklists and assessment of DOHMH Relay program data)

7.1.2 Standard of Care Study Procedures

All patients in the study (Relay arm + SDC are) will receive standard medical care as they would regularly receive in the ED, including a range of relevant substance use services offered at the individual study ED per existing care protocols at each site. These services vary by site and are offered to patients either by clinician discretion or according to specific protocols at each study site. Relevant services vary by site and by patient and may include, but are not limited to: health education, distribution of naloxone kits, universal screening for drug and alcohol use, SBIRT (screening, brief intervention, and referral to treatment), and ED-initiated buprenorphine with outpatient follow-up. Patients also receive standard medical care as they would usually receive in the ED. The exact services vary depending on site- and patient-specific factors and will be captured using patient exit surveys. The study investigators will not attempt to change standard care provided at study sites.

7.1.3 ED Staff and Relay Peer Qualitative Interview Procedures

We will enroll approximately 10-12 ED provider participants and 10 Relay peer navigator participants in qualitative interviews to learn about barriers and facilitators to the intervention model; Interviews will be conducted one-on-one with an interviewer trained in qualitative research techniques. To allow flexibility given the ongoing COVID-19 pandemic, interviews will be conducted either in-person, by phone, or by secure web conferencing (e.g., WebEx). At the qualitative interview contact the interviewer will review the verbal consent script, attain verbal consent for the study and for audio recording, and complete a one-on-one in-depth interview in which the interviewer uses an interview guide. Interviews will be semi-structured, guided by an interview guide (see Interview Guide Attachment), with flexibility to allow for additional questions as needed and to maximize interview flow. Interviews will be digitally recorded and professionally transcribed. As noted previously, any identifying information will be removed from transcripts prior to analysis. Basic characteristics of interview participants (e.g., age, race/ethnicity, gender, job role) will also be recorded, and the interviewer will record field notes at the conclusion of the interview with any additional pertinent observations. Qualitative interview participants will receive an incentive payment at the conclusion of the interview.

7.2 Laboratory Procedures/Evaluations

Not applicable.

7.3 Study Schedule

7.3.1 Screening and Enrollment/Baseline

Screening/Enrollment/Baseline Visit (Visit 1, Day 0)

There is no separate screening visit for this study. Screening for study eligibility will occur during the same ED or hospital visit as the study enrollment / baseline visit. The only patients who are potentially eligible for the study and who will be screened by RAs are those for whom the ED staff has called the Relay program hotline. As part of existing protocols, ED staff at the study sites call the Relay program hotline for patients who have presented to the ED after a nonfatal opioid OD. ED staff are instructed to call the Relay hotline when a patient presents with nonfatal opioid OD, as determined by the treating clinician(s). The Relay hotline is operated by a HIPAA-compliant call center that provides 24-hour service, 365 days/year. It is used by all EDs participating in Relay, including the study sites. ED staff are instructed to call the Relay hotline as soon as they become aware of a patient presenting for nonfatal opioid OD, to help

CONFIDENTIAL

This material is the property of the NYU School of Medicine and NYU Langone Health. Do not disclose or use except as authorized in writing by the study sponsor

Behavioral Intervention Template Version: 11 January 2019

ensure that there is adequate time for both study procedures and (if randomized to the Relay arm) delivery of the Relay intervention.

Assignment of the RA. The Relay hotline operator contacts the appropriate research staff member based on date and time of day according to a call schedule that will be provided to the hotline. The PM/RC/ or RAs will receive information that the Relay hotline routinely collects to facilitate locating the patient in the ED (e.g., patient name, referring provider, location or bed number). The RA will determine whether the patient is already an active Relay participant and/or has already participated in the study and proceed according to study eligibility guidelines. The appropriate RA for the study site will go directly to the ED, arriving within 1 hour (typically within 15-45 minutes depending on study site). Upon arrival, the RA will confirm with ED staff that the patient is medically stabilized (as needed), and then approach the bedside and introduce themselves to the patient. After requesting permission from the patient to provide information about the study, the RA will explain the study procedures and assess eligibility. Clear protocols for RAs will be specified in the study SOP/MOP.

Screening for Eligibility. RAs will follow a standardized series of questions on REDCap using a study iPad (see attachment) to screen patients for study eligibility. If there is any question about a patient's capacity to provide informed consent, RAs will consult the ED treating team (e.g., attending physician) and/or complete the UBACC (see attachment), a brief consent capacity quiz that has been previously validated and used in other ED studies.⁵⁷ If the patient is not eligible for the study, the RA will call the Relay peer navigator to inform him/her of a patient who is not eligible for the study but who could potentially receive Relay services (apart from the study).

Enrollment and informed consent. RAs will enroll and obtain consent from eligible patients for participation in the research activities. The RA will explain the study procedures and incentive schedule, answer any questions, and offer enrollment. Patients will be informed that the decision to participate in the research is voluntary and will not affect the medical care they receive from the ED. If the patient is willing to participate and signs the informed consent form, only then will study staff commence collecting additional information. The informed consent process will be conducted in-person on a study iPad using REDCap (using electronic consent/signature). The participant will be given a paper or e-mailed copy (through REDCap) of the informed consent form and key information sheet. If the patient declines to participate in the study, the RA will call the Relay peer navigator to inform him/her of the patient who has declined to participate in the study but who could potentially receive Relay services (apart from the study, as part of standard DOHMH Relay practice).

Randomization. Patients who meet eligibility criteria and agree to participate in the study will be randomized to the SDC vs. Relay arm. The RA will use an electronic system (REDCap) to create a random assignment to a treatment arm. Randomization uses a 1:1 ratio and is stratified by site; permuted blocks with variable blocks of size 4 and 6 will be used to maintain balance over time and prevent prediction of assignment by the RA. Upon randomization, the RA will immediately inform the participant of the treatment arm assigned. For Relay arm participants, the RA will then inform the Relay peer navigator by phone. If the participant is assigned to the Relay arm, the peer navigator will generally arrive at the ED within 30 minutes.

Baseline data collection. RAs will administer a baseline self-reported assessment. RAs will also collect participant identifying information to allow future linkage with administrative data, and detailed locator form information to enable study staff to contact participants for follow-up assessments. The locator form collects multiple forms of contact information for the individual (e.g., phone numbers, e-mail, social media, addresses, 'hang out' locations) and phone numbers for at least 3 individuals who will know how to reach them in the future. The locator form is based on procedures used successfully by our team in prior studies, and is a crucial component of the retention strategy. RAs will follow procedures to maximize participant privacy. If at any point during baseline data collection an ED provider needs to provide clinical care to the patient, the RA will pause study procedures so as not to interfere with clinical care.

Because participant identifiers and locator form information are not sensitive to the Relay intervention, RAs can collect this information at the time that is most appropriate to maximize patient flow and ensure

CONFIDENTIAL

This material is the property of the NYU School of Medicine and NYU Langone Health. Do not disclose or use except as authorized in writing by the study sponsor

Behavioral Intervention Template Version: 11 January 2019

peer navigators can engage patients. As much as possible, RAs will complete the baseline assessment prior to participant receipt of the Relay intervention (for participants in the Relay arm).

Administration of Relay intervention or SDC. Relay peer navigators will deliver the ED portion of the Relay intervention for participants in the Relay arm. For participants in the SDC arm, RAs will ensure that, at a minimum, participants receive (from the RA) OEND, a list of treatment programs, and an informational handout about Relay. RAs will document the number of naloxone kits (1-2) distributed as described in Section 14.1. Participants will receive other site-directed care as specific to the particular ED and/or care provider (not under the control of the study). See other sections of this protocol for a detailed description of the Relay intervention and SDC conditions.

Exit survey. Near the end of the ED stay, the RA will complete an exit survey recording what intervention elements were received by participants. If needed (for example, in instances where the ED visit spans many hours), the RA may complete the exit survey by phone with the participant the day following the ED visit.

Wrap up. RAs will schedule the first follow-up assessment and will give participants a study contact card with the appointment information and information on how to contact the study team. Participants will be given the study incentive payment and a FAQ document about the Greenphire ClinCards. Within the week following the baseline visit the participant will be mailed a thank you card.

Hybrid Baseline visits due to COVID-19

Due to COVID-19, baseline visits may be conducted in a hybrid manner in order to minimize staff time in the ED. In this instance, RAs would screen, enroll, consent, and randomize patients in person in the ED. They would then conduct the survey section of the baseline visit virtually from a private office location adjacent to the ED using iPads (one iPad will be handed to the participant) using video conferencing with a secure, HIPAA compliant platform (WebEx).

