| Population | Adults (≥ 18 years), English- or Spanish-speaking, presenting to a participating ED with nonfatal opioid OD |
| Study Sites | Study sites are three health systems, representing four high-volume NYC hospital EDs. The sites are geographically dispersed and serve patient populations that are diverse with respect to age, sex, race, and ethnicity. 
1. NYU Langone Health – Tisch Hospital & NYU Langone Hospital—Brooklyn2. Mount Sinai Beth Israel3. St. Barnabas Hospital |
| Number of participants | 350 participants expected to be enrolled in the RCT across 3 health system EDs (4 EDs total). Approximately 10-12 ED provider participants, approximately 10 Relay peer navigator participants, and approximately 12 patients will complete qualitative interviews. |
| Description of Study Intervention/Procedure | Relay is a novel program that engages and intervenes with individuals in the ED following an opioid OD and for the next 90 days, with the goal of preventing subsequent OD events. Relay is delivered by trained peer navigators, who are DOHMH staff with lived substance use experience. Relay navigators provide counseling, linkage to services, and OD prevention education. |
| Reference Therapy | Site-directed care (SDC): site-specific existing interventions delivered to patients with OUD as part of ED care. At a minimum SDC arm patients will receive OD education and naloxone distribution (OEND), a list of opioid treatment programs, and an informational flyer about Relay. |
| Key Procedures | Survey administration, education and counseling (for Relay arm), qualitative interviews |

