10.6 Measures to Minimize Bias

10.6.1 Enrollment/Randomization/Masking Procedures

At the enrollment visit, the RA will use an electronic system (REDCap) to trigger assignment to a treatment arm. Randomization will use a 1:1 ratio and is stratified by site; permuted blocks with variable blocks of size 4 and 6 will be used to maintain balance over time and prevent prediction of assignment by the RA. Upon randomization, the RA will immediately inform the participant of the treatment arm assigned.

While the RA conducting the baseline assessment cannot be blinded to the intervention assignment (since it will occur during the same ED visit as the intervention), whenever possible a different RA will be assigned to conduct follow-up interviews in an attempt to maintain blinding. Blinding may be imperfect since participants may reveal their intervention assignment, including based on their answers to the follow-up assessments. Participants themselves cannot be blinded to the treatment condition due to the nature of the intervention. Study staff conducting the administrative data abstraction for the primary study outcomes will be blinded to the intervention assignment. Study analytic staff are blinded to treatment condition until the conclusion of the trial and finalization of the analytic database.

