The participant and the person obtaining informed consent will sign and date the informed consent document prior to any procedures being done specifically for the study. A copy of the signed electronic consent will be provided to the potential participant in one of three ways as described above. The electronic copy of the signed informed consent document will be stored electronically in the subject's research record.

The consent process, including the name of the individual obtaining consent, will be thoroughly documented in the subject's research record. Any alteration to the standard consent process and the justification for such alteration will likewise be documented. Regular audits will be performed to ensure that consent forms are fully and properly completed for all study participants.

Participant capacity and comprehension: Potential participants will be required to demonstrate adequate comprehension of the study and decision-making capacity to participate in the study. Only patients who have the capacity to give informed consent will be included in the study. Patients will not be included if they are too acutely intoxicated to give informed consent or otherwise medically unfit to participate, as determined by trained study staff. If there is any question about the patient's capacity to provide informed consent, study staff will: a) ask ED clinical providers (e.g., physician, nurse) for advice about whether the participant has capacity to provide consent, and/or b) complete formal assessment of decisional capacity for participation in research using the University of California, San Diego Brief Assessment of Capacity to Consent (UBACC). The UBACC has been previously validated and generally takes less than 5 minutes to administer.

Consent for Qualitative Interviews:

Patient participants, ED providers, and Relay Wellness Advocates will verbally consent to take part in the qualitative interview. The Qualitative Researcher will review the IRB-approved verbal consent form in English with each participant. The Qualitative Researcher will review a description of the study, a description of potential risks and benefits, a statement of confidentiality, and an indication of the right to refuse or withdraw participation at any time without any consequence the study requirements. The verbal consent will include explicit consent for an audio recording.

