We will be providing a list of participant names and birthdates of people who have participated in the SDC arm to the Relay hotline call center. The call center will not be provided with any other participant information. Using a secure, password protected file transfer portal that only NYU and the Relay hotline call center will have access to, the PM or RC will transfer the list of participant names. This information will be provided securely to the Relay hotline call center because there is not a study RA on call 24/7 and therefore the call center needs an alternate way of knowing when a patient for whom Relay is activated is in the study SDC arm meaning a Wellness Advocate should not be dispatched to visit the patient (because this would cause crossover between study arms). This will only be relevant in the rare instances for which a study participant in the SDC arm has a repeat overdose visit to an emergency department participating in the study and the Relay hotline is called. In these cases a study RA will conduct an unscheduled visit or follow-up visit as appropriate (see Section 7.3) in the ED once available (if the participant remains in the ED) or will attempt to follow up by phone. The Relay hotline call center activities related to this study follow a comprehensive data privacy and security agreement with the NYC Department of Health and Mental Hygiene, which specify data security procedures, rules against data sharing, and other protections for privacy of the data. The Relay hotline call center will delete all participant lists after completion of the study follow-up period, one year after enrollment of the last study participant.

The study PIs will have ultimate responsibility for overseeing data collection and management. The PIs are responsible for ensuring the accuracy, completeness, legibility, and timeliness of the data reported.

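### Site-stratified blocks of 4 and 6 limit but do not prevent prediction by the research assistant: at most about 69% of assignments could be guessed, fewer if not all earlier ones are seen

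*Combined protocol and SAP*

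**What the plan says.** Section 7.3.1 (Randomization) states that "Randomization uses a 1:1 ratio and is stratified by site", and that "variable blocks of size 4 and 6 will be used to maintain balance over time and prevent prediction of assignment by the RA". Section 10.6.1 repeats the claim in the same words. The RA triggers the assignment in REDCap after signed consent, and "Upon randomization, the RA will immediately inform the participant of the treatment arm assigned". Section 10.6.1 accepts that "the RA conducting the baseline assessment cannot be blinded to the intervention assignment".

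The same RA acts before randomisation: approaching the patient, running the eligibility screen and obtaining consent (Section 7.3.1). Section 13.3.2 excludes patients who are too intoxicated to consent or "otherwise medically unfit to participate, as determined by trained study staff". When a patient is ineligible or declines, the RA tells the Relay peer navigator, who may offer Relay outside the study (Section 7.3.1).

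On who attends each patient, Section 7.3.1 says that "The Relay hotline operator contacts the appropriate research staff member based on date and time of day according to a call schedule". The documents do not say whether RAs can see assignments made by colleagues, or whether the block sizes are kept from them.

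**The concern.** The plan credits the design with a property that permuted blocks do not have. Within each block the arm that is behind becomes more likely, and the smaller the blocks, the stronger the clue. Stratifying by site gives each site its own short sequence, and allocation is open, so the person who enrols the next patient knows at least the assignments that they made themselves.

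Concealing the assignment until after consent does not remove the problem, because the judgement about whom to approach, whom to consider fit and how to present the study comes earlier. An RA who expects site-directed care next, and thinks that this patient needs Relay, has a route to Relay that avoids randomisation. If that happened, the arms would differ in who was enrolled. Intention-to-treat analysis, adjustment for site and blinded abstraction of administrative data would not correct such a difference.

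**Working it through.** The plan gives no predictability figure, so there is none to reproduce.

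**Inputs.** Ratio 1:1, stratified by site, block sizes 4 and 6 (Sections 7.3.1 and 10.6.1); 350 participants in 4 emergency departments of 3 health systems (Protocol Summary), so about 350/4 = 88 or 350/3 = 117 per stratum. Assumed: equal split over sites, equal mix of the two sizes, and the share of the site's earlier assignments that the RA sees.

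**Step 1: exact, full history, no knowledge of block sizes.** The simple rule is to guess the arm that is behind and toss a coin when the arms are level. For a block of size 2m the expected number of correct guesses is m + (4^m / C(2m, m) − 1)/2.
- Size 4: 2 + (16/6 − 1)/2 = 2.833, or 70.8%.
- Size 6: 3 + (64/20 − 1)/2 = 4.1, or 68.3%.
- Equal mix: (2.833 + 4.1)/10 = 69.3%.

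**Step 2: simulation, sizes known, varying history.** The RA's probabilities are updated over the possible block size and the places left in it. Seen assignments are taken as a random share of the site's sequence.

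| Share of site history seen | Correct guesses | Called with at least 75% certainty |
|---|---|---|
| 100% | 69% | 49% |
| 75% | 63% | 20 to 21% |
| 50% | 59% | 6 to 7% |
| 25% | 55% | 1% |
| Chance | 50% | 0% |

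With full history about 5 to 6% of assignments are known for certain. Strata of 88 and of 117 give the same results.

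**Step 3: value of hiding the sizes.** With full history, none for the rate of correct guesses: the rule in Step 1 already reaches 69%. With part of the history it helps. Against that same rule, correct guesses fall from about 63% to 56% when 75% is seen, and from about 59% to 53 to 54% when half is seen.

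**Step 4: larger blocks.** With sizes varying over 8 to 16 and full history, about 64% of guesses are correct, about 13% of assignments can be called with at least 75% certainty, and 0.4% are certain.

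**Step 5: illustrative bias.** Let a be the share of correct guesses and s the relative difference in event rate between patients enrolled when the RA expects one arm and those enrolled when the RA expects the other. If lower-risk patients are steered to Relay, a true incidence rate ratio (IRR) of 1 becomes [1 − s(a − 0.5)] / [1 + s(a − 0.5)]. If higher-risk patients are steered there, it becomes the inverse.
- a = 0.69, s = 0.10: 0.981/1.019 = 0.96, or 1.04.
- a = 0.69, s = 0.20: 0.962/1.038 = 0.93, or 1.08.
- a = 0.59, s = 0.10: 0.991/1.009 = 0.98, or 1.02.

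The planned effect in Section 10.5 is 1.52/2.0 = 0.76. On the log scale, the first case is 0.038/0.274 = 14% of it and the third 0.018/0.274 = 7%. The values of s are illustrations; nothing in the documents fixes them.

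**The case against.** Variable permuted blocks, assigned electronically after signed consent, are a recognised design, and several points count against a harsher reading.

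- **Full history is not shown.** A reader might infer that any unblinded RA can guess 69%. That needs every earlier assignment at the site. RAs are called by schedule, no section says that they share assignments, and Section 10.6.1 plans a different RA for follow-up interviews where possible, to keep that RA blind. This stands: 69% is a ceiling.
- **RAs are not shown to work from the printed sizes.** Section 7.3.1 says that RA procedures will be in the SOP/MOP, and no section says that those contain block sizes. This also stands. It is equally true that no section keeps the sizes from RAs.
- **Discretion is limited.** Emergency department staff start the process by calling the hotline. Screening uses standard questions in REDCap. Doubts about capacity go to ED clinicians and/or the UBACC (Section 13.3.2). Section 12 has weekly review of numbers approached and of eligibility classifications, Section 10.4.5 tracks reasons for ineligibility and refusal, and the DSMB reviews adherence to randomisation (Section 8.8). These controls limit and expose selective enrolment, but they do not conceal the next assignment.
- **Direction.** A reader might infer a bias in favour of Relay. The documents do not support a direction: steering the neediest patients to Relay would hide a benefit.
- **The remedy is partial.** Blocks of 8 to 16 still allow up to 64% correct guesses with full history. The larger gain is in confident calls, from 49% to about 13%.

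**Conclusion.** The point holds in a limited form. The stated purpose, preventing prediction, is not achieved by this scheme; limiting prediction is. The ceiling is about 69% correct, with about half called at 75% certainty or more. With half or a quarter of the site's history seen, correct guesses fall to about 59% or 55%. These figures assume known sizes and an equal mix of 4 and 6. Which row applies cannot be settled from the documents.

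Any resulting bias could go either way and is probably small beside the planned effect: about 14% of it on the log scale for a 10% risk shift with full history, if the RA acts on every guess. Nothing in the documents suggests that an RA has done or would do so. This is a minor matter, worth correcting because the correction is cheap and the present wording could lead readers to think that concealment is complete.

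**What to change.** In Sections 7.3.1 and 10.6.1, replace the sentence with wording such as: *permuted blocks of randomly varying size, with sizes held only by the statistician who builds the REDCap table, to limit prediction of assignment*. Keep the sizes out of every document that RAs can see.

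Because 4 and 6 are already printed, build the table, or the part not yet used, with new undisclosed sizes over a larger and wider range. The range 8 to 16 is given here only to show the gain; the sizes actually used should not appear in the protocol.

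**Cost.** Two edited sentences and one REDCap allocation table. The largest possible imbalance within a site rises from 6/2 = 3 to about 16/2 = 8. Even if all four emergency departments were separate strata and ended at the extreme in the same direction, the arms would be 191 and 159. The variance factor would be (1/191 + 1/159)/(2/175) = 1.008, a loss of under 1%. Site is already in the primary model (Section 10.4.2), so imbalance between sites is handled in the analysis.
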